7 ABBREVIATIONS

AE	Adverse Event
AMP	Adenosine Monophosphate
AUC	Area Under the Curve
BSA	Body Surface Area
C _{max}	Maximum Concentration
COPD	Chronic Obstructive Pulmonary Disease
CRF	Case Report Form
CTCAE	Common Terminology Criteria for Adverse Events
DNA	Deoxyribonucleic Acid
ECG	Electrocardiography
ERB	Ethics Review Board
FDA	U.S. Food and Drug Administration
GCP	Good Clinical Practices
HC	Health Canada
HCA	Alpha-Hydroxycinnamaldehyde
HPRT	Hypoxanthine-guanine Phosphoribosyl Transferase
IB	Investigational Brochure
IC50	Half Maximal Inhibitory Concentration
ICF	Informed Consent Form
ICH	International Conference on Harmonisation
IGA	Investigator Global Assessment
IND	Investigational New Drug
IRB	Institutional Review Board
IVRT	In Vitro Release Testing
mcg	Microgram
MedDRA	Medical Dictionary for Regulatory Activities
mL	Milliliter
MMRM	Mixed Model for Repeated Measures
MTD	Maximum Tolerated Dose
NCI	National Cancer Institute
NIH	National Institutes of Health
NOAEL	No Observed Adverse Effect Level
NDA	New Drug Application
ng	Nanogram
PDE-4	Phosphodiesterase 4
PK	Pharmacokinetics

QD	Once Daily ("quaque die")
SAE	Serious Adverse Event
Th1	Type 1 T Helper Cell
Th17	Type 17 T Helper Cell
T _{max}	Time to reach maximum concentration
TPA	Target Plaque Area
TPSS	Target Plaque Severity Score
TPSS x TPA	Target Plaque Severity Score x Target Plaque Area
V79	Chinese hamster cell line

8 BACKGROUND AND RATIONALE

8.1 Introduction

Roflumilast is a phosphodiesterase 4 (PDE-4) inhibitor approved globally to reduce the risk of chronic obstructive pulmonary disease (COPD) exacerbations associated with chronic bronchitis. Roflumilast and its active metabolite, roflumilast N-oxide, are high affinity selective inhibitors of PDE-4 (a major cyclic-3',5'-adenosine monophosphate (cyclic AMP)-metabolizing enzyme), whose activity leads to accumulation of intracellular cyclic AMP. There are four different subtypes of PDE-4: PDE-4a, PDE-4b, PDE-4c, and PDE-4d, each with several isoforms (splicing variants). IC₅₀ values of both roflumilast and roflumilast N-oxide for the different PDE-4 isoforms and subtypes are mostly sub-nanomolar and single digit nanomolar ([Hatzelmann 2010](#)). The PDE-4 family of enzymes are the most prevalent phosphodiesterases in immune cells and inhibition of PDE-4 subtypes has been associated with anti-inflammatory effects in many biological systems.

Psoriasis is a chronic inflammatory skin disease characterized by raised, well-demarcated, erythematous oval plaques with adherent silvery scales. Numerous past reports have suggested a deficiency of cyclic AMP-dependent protein kinases in human psoriatic skin ([Brion 1986](#)). More recently, various cytokines produced by Th1 and Th17 cells have been shown to play a crucial role in the pathogenesis of psoriasis. It has been postulated that the anti-inflammatory effects of PDE-4 inhibitors may provide a beneficial therapeutic intervention in the treatment of chronic plaque psoriasis.

The past 15 years have witnessed a transformation in the systemic treatment of moderate to severe psoriasis with the advent of biological therapies. However, for patients with milder forms of disease, best treated with topical options, the therapeutic landscape really has not changed in several decades. Topical steroids come in all shapes and forms, but the lower potency steroids are not effective and the higher potency steroids are beset with issues of local skin atrophy and the potential for hypothalamic-pituitary axis suppression when applied over larger body surface areas and for prolonged periods of time. Vitamin D has been the other staple of topical treatment but it is irritating, not suitable for use on the face, and its efficacy is rather modest. Hence, there is substantial medical need for additional topical approaches in the treatment of psoriasis.

8.1.1 Preclinical Studies

Roflumilast was initially developed as a 500 mcg tablet for oral therapy in patients with COPD, and as such has been thoroughly evaluated in nonclinical studies. The safety profile is well-established and the results of those studies are relevant to the dermal roflumilast (ARQ-151 cream) development program. Oral roflumilast (500 mcg tablet) was approved by Health Canada as DAXAS® in December 2010 and by the US FDA as DALIRESP® in February 2011 for the treatment of COPD. The study sponsor is conducting nonclinical studies in which roflumilast is applied dermally to supplement the information available through the registration and labeling of oral roflumilast and specifically to support initial dermal clinical trials. Summaries of these new data from dermal studies and existing data from the prior oral/systemic studies follow. In addition, since roflumilast N-oxide is a major active metabolite, some studies were conducted on the metabolite also.

The dermal nonclinical program for ARQ-151 cream followed current International Conference on Harmonisation (ICH) guidelines. A dermal toxicology program was initiated that included a 13-week dermal toxicity study in minipigs (with a 28-day interim sacrifice to support Phase 1 studies), a skin sensitization study in guinea pigs, a phototoxicity study and an eye irritation study.

© 2006 by the author. All rights reserved.

For more information, contact the Office of the Vice President for Research and Economic Development at [contact] or [contact].

A thick black horizontal bar at the bottom of the page, likely a redacted section of text.

11. *What is the primary purpose of the following statement?*

A horizontal bar chart with four bars of increasing height from left to right, representing data values. The bars are black and set against a white background.

For more information, contact the Office of the Vice President for Research and Economic Development at [contact] or [contact].

© 2019 Pearson Education, Inc.

[REDACTED]

[REDACTED]

[REDACTED]

[REDACTED]

10 of 10

© 2013 Pearson Education, Inc. All Rights Reserved. May not be copied, scanned, or duplicated, in whole or in part. Due to electronic rights, some third party content may be suppressed from the eBook and/or eChapter(s). Editorial review has determined that any suppressed content does not materially affect the overall learning experience. Pearson Education, Inc. reserves the right to remove additional content at any time if subsequent rights restrictions require it.

© 2013 Pearson Education, Inc.

© 2019 Pearson Education, Inc.

1. *What is the primary purpose of the study?*

For more information, visit www.ams.org or call [contact].

© 2013 Pearson Education, Inc.

© 2019 Pearson Education, Inc.

Digitized by [contact]

Digitized by [contact]

For more information, contact the Office of the Vice President for Research and Economic Development at [contact] or [contact].

© 2019 Pearson Education, Inc.

© 2013 Pearson Education, Inc.

For more information, contact the Office of the Vice President for Research and Economic Development at [contact] or [contact].

Digitized by [contact]

© 2013 Pearson Education, Inc.

For more information, contact the Office of the Vice President for Research and the Office of the Vice President for Student Affairs.

For more information, contact the Office of the Vice President for Research and Economic Development at [contact] or [contact].

© 2019 Pearson Education, Inc.

For more information, contact the Office of the Vice President for Research and the Office of the Vice President for Student Affairs.

For more information, contact the Office of the Vice President for Research and Economic Development at [contact] or [contact].

Digitized by [contact]

A large grid of black bars on a white background, likely a placeholder or redacted content. The grid consists of approximately 20 horizontal rows and 10 vertical columns of varying bar lengths. The bars are solid black and have thin white borders. Some bars are very long, while others are very short, creating a pattern of horizontal and vertical lines across the page.

[REDACTED]

[REDACTED]

[REDACTED]

[REDACTED]

[REDACTED]

[REDACTED]

8.1.2 Clinical Studies

This will be the first study of topical ARQ-151 cream in the human population.

However, oral roflumilast (DALIRESP®, DAXAS®) has been approved globally for the treatment of COPD and has been evaluated in nine Phase III/IV randomized double-blind clinical trials ([Wedzicha 2016](#)). Overall, the safety of oral roflumilast has been well established in its targeted population of mostly middle- and upper-aged individuals who currently smoke cigarettes or have smoked them extensively in the past. Adverse events (AEs) reported with roflumilast tablets have been consistent with those expected for oral PDE-4 inhibitors. In a pooled analysis of safety data from 6-month and 1-year clinical trials (N=8630), the most common AEs were diarrhea, weight loss and nausea. Other AEs reported more frequently with roflumilast treatment than with placebo were back pain, influenza, insomnia and decreased appetite ([Michalski 2012, Wedzicha 2016](#)).

In addition to the self-reported cases of weight loss in the 6-month and 1-year trials, clinically significant weight loss was also reported in two prospective studies that evaluated weight ([Michalski 2012](#)).

Psychiatric-related AEs were also greater in patients treated with roflumilast tablets (5.9%) compared to those treated with placebo (3.3%). The most common psychiatric-related AEs were insomnia, depression and anxiety. A small number of cases of completed suicide and suicide ideation have been reported in patients taking oral roflumilast in clinical trials and also during post-marketing experience ([Michalski 2012](#)).

The only contraindication to oral roflumilast, other than hypersensitivity to components of the product, is in patients with moderate to severe liver impairment (Child-Pugh B or C), where systemic levels of roflumilast may become highly elevated.

8.2 Rationale

In 2016, Snape and colleagues performed a phase 1 randomized clinical trial to assess the effect on skin infiltrate thickness and tolerability of topical phosphodiesterase inhibitors, including roflumilast, in the treatment of psoriasis vulgaris using a modified psoriasis plaque test. The products evaluated were the active comparators calcipotriol 0.005% and betamethasone valerate 0.1% (both in their marketed cream formulations), and investigational cream formulations of roflumilast 0.5%, TAK-084 0.5% and 5%. A vehicle cream was used as a control (the vehicle cream and roflumilast formulations in this study were different from the ARQ-151 cream formulation). Each treatment was applied daily to different test sites located on a single psoriasis plaque of an individual for 3 weeks. Fifteen patients with psoriasis were studied. The primary endpoint of mean change from baseline in skin infiltrate thickness after 3 weeks of treatment

showed statistically significant improvements for all treatments: betamethasone valerate (-286.9 µm), the selective PDE-4 inhibitors roflumilast 0.5% (-237.1 µm), TAK-084 0.5% (-153.6 µm), TAK-084 5% (-216.7 µm) and calcipotriol 0.005% (-187.7 µm) when compared with vehicle cream control (all $p < 0.001$) (Snape 2016).

The above data indicated to us that topical roflumilast, in an appropriate market image vehicle, could provide an important addition to the dermatologist's armamentarium in treating chronic plaque psoriasis.

8.2.1 Dose Selection

The ARQ-151 cream 0.5% dose concentration was selected because of the efficacy observed in the Snape, et al study described above ([Snape 2016](#)). [REDACTED]

The dose concentration of ARQ-151 cream 0.15% was selected to determine whether lower ARQ-151 cream doses are effective and whether systemic exposure is also reduced.

Cohort 1 will involve application of ARQ-151 cream 0.5% to 25 cm² of psoriatic plaque(s). It is well known that cutaneous disease states can alter drug permeability as compared to normal human skin. Since psoriatic skin is known to have different drug permeability characteristics than normal skin ([Tang-Liu 1999](#)), we do not believe there is anything to be gained by prior application of topical drug to normal human volunteers. [REDACTED]

8.2.2 Risks and/or Benefits to Subjects

Subjects in Cohort 1 will not be expected to see an improvement in their psoriasis since it is a single dose of drug product and the purpose of Cohort 1 is PK analysis to justify the escalation in the area treated in Cohort 2.

Subjects randomized to active treatment in Cohort 2 may see an improvement in their psoriasis with the use of ARQ-151 cream at either or both dose levels. Subjects randomized to the vehicle arm may also see an improvement as the excipients in the vehicle may have a moisturizing effect on the subject's psoriatic plaques. ARQ-151 cream is an unprecedented treatment for psoriasis and if efficacious, would add substantially to the dermatologist's armamentarium in treating patients with this disease.

The safety monitoring practices employed in this protocol (i.e., physical examinations, application site reaction assessments, hematology, serum chemistry, urinalysis, and AE questioning) are adequate to protect the subjects' safety and should detect expected AEs. [REDACTED]

[REDACTED]

8.3 Study Objectives

8.3.1 Primary Objectives

1. To assess the safety and PK of a single dose application of ARQ-151 cream 0.5% to 25 cm² of psoriatic plaque(s) (Cohort 1).
2. To assess the safety, pharmacokinetics and efficacy of ARQ-151 cream 0.5% and ARQ-151 cream 0.15% vs. vehicle applied QD x 28 days to individuals treated with up to 5.0% BSA of chronic plaque psoriasis (Cohort 2).

8.4 Efficacy Endpoints

8.4.1 Primary Endpoint

The single dose Cohort 1 will have analyses only for safety and pharmacokinetics.

The parallel group assessment (Cohort 2) will have analyses for safety, pharmacokinetics, and efficacy.

In the parallel group assessment (Cohort 2), the Primary Efficacy Endpoint will be:

- Difference in mean percent change from baseline at week 4 in the product of: [Target Plaque Severity Score (TPSS) x Target Plaque Area (TPA)] (TPSS x TPA) between each dose concentration level of ARQ-151 cream and vehicle control. This will be assessed as a sum of up to 3 target plaques per subject.

8.4.2 Secondary Endpoints

The secondary efficacy endpoints in the parallel group (Cohort 2) assessment will include:

1. Difference in mean percent change from baseline at weeks 1, 2, and 3 in TPSS x TPA between each dose concentration level of ARQ-151 cream and vehicle control. This will be assessed as a sum of up to 3 target plaques per subject.
2. Difference in mean percent change from baseline at weeks 1, 2, 3, and 4 in TPSS between each dose concentration level of ARQ-151 cream and vehicle control. This will be assessed as a sum of up to 3 target plaques per subject.
3. Difference in mean percent change from baseline at weeks 1, 2, 3, and 4 in TPA between each dose concentration level of ARQ-151 cream and vehicle control. This will be assessed as a sum of up to 3 target plaques per subject.

8.5 Overall Study Design and Plan

There are 2 cohorts of subjects:

Cohort 1 is a single dose study to 25 cm² of psoriatic plaque(s) in up to up to 8 psoriasis subjects. Cohort 1 subjects may then be enrolled into Cohort 2 of the study if all admission criteria are met at the Baseline Visit (Day 1, Visit 2, per Cohort 2). In this case, the same plaque(s) treated in the Cohort 1 study may also be treated in Cohort 2.

Cohort 2 is a parallel group, double blind, vehicle controlled study in which ARQ-151 cream 0.5%, ARQ-151 cream 0.15% or vehicle cream is applied QD x 28 days to subjects with between 0.5% to 5.0% BSA of chronic plaque psoriasis.

Including both Cohorts, a total of up to 92 subjects will be enrolled at 7 study sites in Canada and 1 site in the U.S. Subjects will be adult (≥ 18 y/o) males or females with chronic plaque psoriasis. For inclusion into Cohort 2, subjects must have at least 1 target plaque of at least 9 cm² in size with TPSS ≥ 4 . While 1 target plaque is minimally acceptable, it is strongly recommended that 2 or 3 target plaques be identified, if present, meeting these criteria. Target plaques may be on the knees and/or elbows, but priority should be given to identifying target lesions in other areas. All psoriasis lesions on a subject will be treated in this Cohort except for those on the face, scalp, intertriginous areas, palms and soles.

Subject Participation

Cohort 1: This cohort involves a minimum of three clinic visits including Screening, Baseline, one follow-up visit (24 hours after the baseline visit) and one follow up telephone call 7 days after the follow up visit. Subjects may be asked to return for additional visits(s) if an adverse reaction occurs. The interval between the Screening and Baseline visits could be up to 14 days, therefore the anticipated maximum duration of subject participation in Cohort 1 is 22 days.

Cohort 2: This cohort involves a minimum of seven clinic visits including Screening, Baseline and four visits at Week 1, Week 2, Week 3 and Week 4 of treatment and a day 29 visit for a final PK collection. A follow-up telephone call with subjects will occur at week 5 to assess any reactions to discontinuing drug product and will decide upon disposition of any ongoing adverse events.

The interval between the Screening and Baseline visits could be up to 6 weeks, therefore the anticipated maximum duration of subject participation in Cohort 2 is 77 days.

8.6 Randomization

Cohort 1: Cohort 1 is an open label single dose application of ARQ-151 cream 0.5% to 25 cm² of psoriatic plaque(s) in up to eight (8) subjects. Cohort 1 subjects may enroll in Cohort 2 if the eligibility criteria for Cohort 2 are met.

Cohort 2: Subjects will apply ARQ-151 cream 0.5% or ARQ-151 cream 0.15% or vehicle to psoriatic plaques that will not exceed an application area of 5% BSA. Assignment of drug or vehicle will be made at a 1:1:1 ratio according to a computer generated randomization list. Randomization will take place at Baseline after the patient has been found to be fully eligible for participation. A kit containing ten (10) tubes of study medication will be assigned to each subject. Each kit has a unique kit number (randomization number).

8.7 Numbering of Subjects

All treated subjects will be identified by a unique four-digit subject ID number. The first two digits correspond to the site number (assigned by the Sponsor), the next three digits correspond to the sequential order in which the subject was enrolled into the study. Screen failures will not be assigned a number.

The clinical site is responsible for maintaining a current log of subject ID number assignments and the kit number assigned to that subject. The subject's initials (first/middle/last) and ID number are required to be entered on all clinical study documentation (e.g., case report forms, labeling of clinical materials and sample containers, investigational product accountability logs, etc.).

8.8 Blinding

Cohort 1: This is an open label Cohort, therefore both the subjects and the clinical personnel will be aware that ARQ-151 cream 0.5% will be applied to 25 cm² of psoriatic plaque(s).

Cohort 2: This is a double-blind Cohort, therefore neither the subjects nor the clinical personnel will be aware of which treatment an individual has received.

8.9 Selection of Study Population

8.9.1 Inclusion Criteria

Subjects must fulfill all of the following inclusion criteria to be eligible for participation in the study:

1. Participants legally competent to sign and give informed consent
2. Cohort 1: Adult male and female subjects aged ≥ 18 years with at least 25 cm² of chronic plaque psoriasis (diagnosed by a dermatologist).
3. Cohort 2: Adult male and female subjects aged ≥ 18 years with chronic plaque psoriasis (diagnosed by a dermatologist) covering 0.5% to 5.0% of total BSA excluding the face, scalp, intertriginous areas, palms and soles.

4. Subjects must have at least one target plaque, of at least 9 cm² in size with a TPSS ≥ 4 . Target plaques may be on the knees and/or elbows, but priority should be given to identifying target lesions in other areas. All psoriasis lesions on a subject will be treated in this study except for those on the face, scalp, intertriginous areas, palms and soles.
5. Psoriasis disease duration of ≥ 6 months at the baseline visit.
6. Women of childbearing potential (WOCBP) must have a negative urine pregnancy test at Screening (Visit 1). In addition, sexually active WOCBP must agree to use at least one form of highly effective contraception throughout the trial. Highly effective forms of contraception include: oral/implant/injectable/transdermal contraceptives, intrauterine device, and partner's vasectomy. If barrier methods are used (e.g., condom with spermicide, diaphragm with spermicide), then 2 forms of conception are required.
7. Women of non-childbearing potential (WONCBP) must either be post-menopausal with spontaneous amenorrhea for at least 12 months with a serum follicle stimulating hormone (FSH) level of ≥ 30 mIU/mL or have undergone surgical sterilization (permanent sterilization methods include hysterectomy, bilateral oophorectomy, hysteroscopic sterilization, bilateral tubal ligation or bilateral salpingectomy).
8. In good health as judged by the Investigator, based on medical history, physical examination, 12-lead electrocardiogram (ECG), serum chemistry labs, hematology values, and urinalysis.
9. Subjects agree not to have prolonged sun exposure during the course of the study. Tanning bed use is not allowed.
10. Subjects are considered reliable and capable of adhering to the Protocol and visit schedule, according to the judgment of the Investigator.

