5 SYNOPSIS

Compound:	ARQ-151 cream 0.15 % and ARQ-151 cream 0.5%
Clinical Indication:	Chronic Plaque Psoriasis
Study Phase and Type:	A Phase 1/2a Single Dose and 28-day Parallel Group, Double Blind, Vehicle-Controlled Study of the Safety, Pharmacokinetics and Efficacy of ARQ-151 cream 0.5% and 0.15% in Adults with Mild to Moderate Chronic Plaque Psoriasis
Study Objectives:	
1. To assess the safety and PK of a single dose application of ARQ-151 cream 0.5% to 25 cm² of psoriatic plaque(s) (Cohort 1)2. To assess the safety, pharmacokinetics and efficacy of ARQ-151 cream 0.5% vs. vehicle and ARQ-151 cream 0.15% vs vehicle applied QD x 28 days to individuals with 0.5% to 5.0% BSA of chronic plaque psoriasis (Cohort 2)
Summary of Study Design:	
There are 2 cohorts of subjects.
 
Cohort 1 is a single dose study to 25 cm² of psoriatic plaque(s) in 8 psoriasis subjects. Cohort 1 subjects will then be enrolled, if they meet entry criteria, into Cohort 2 of the study.
 
Cohort 2 is a parallel group, double blind, vehicle controlled study in which ARQ-151 cream 0.5%, ARQ-151 cream 0.15% or vehicle cream is applied QD x 28 days to subjects with at least 0.5% BSA of chronic plaque psoriasis; area for application will not exceed 5.0% BSA.

Blinding:	
The single dose assessment (Cohort 1) to 25 cm² of psoriatic plaque(s) is open label.
 
The parallel group study (Cohort 2) is double blind and vehicle controlled.

Countries:	Canada (Cohorts 1 and 2) and United States (Cohort 2 only)
Number of sites:	7 sites in Canada; 1 site in the United States.
Study Population:	Subjects will be adults, male and female (>18 y/o). Cohort 1 subjects will have at least 25 cm ² of chronic plaque psoriasis; Cohort 2 subjects will have 0.5 – 5.0% total BSA of chronic plaque psoriasis and at least one target plaque of psoriasis at least 9 cm ² in size and with a TPSS ≥ 4.
Number of Subjects:	
1. Cohort 1 = Up to 8 subjects2. Cohort 2 (can include Cohort 1 subjects) = 84 subjects; randomized 1:1:1 to ARQ-151 cream 0.5%: ARQ-151 cream 0.15%: vehicle/placebo. Total subjects in both cohorts = 84-92.

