8.9.2 Exclusion Criteria

1. Subjects with non-plaque forms of psoriasis (erythrodermic, guttate, pustular or palmo-plantar psoriasis)
2. Subjects with drug-induced psoriasis
3. Evidence of skin conditions at the time of Screening Visit other than psoriasis that would interfere with evaluations of the effect of the study medication on psoriasis, as determined by the Investigator
4. Subjects with any serious medical condition or laboratory abnormality, that would prevent study participation or place the subject at significant risk, as judged by the investigator
5. Subjects with any psychiatric illness that would prevent study participation or place the subject at significant risk, as judged by the investigator
6. Pregnant or lactating women or women planning to become pregnant during the study and / or within 28 days following the last dose of study medication
7. Known allergies to excipients in ARQ-151 cream (petrolatum, isopropyl palmitate, methylparaben, propylparaben, Diethylene Glycol Monoethyl Ether, hexylene glycol, cetylstearyl alcohol, dicetyl phosphate and ceteth-10 phosphate)

8. Subjects who cannot discontinue the use of strong P-450 cytochrome inducers e.g., efavirenz, nevirapine, glucocorticoids, barbiturates (including phenobarbital), phenytoin, and rifampin for two weeks prior to the baseline visit and during the study period.
9. Subjects who cannot discontinue the use of strong P-450 cytochrome inhibitors e.g., indinavir, nelfinavir, ritonavir, clarithromycin, itraconazole, ketoconazole, nefazodone, saquinavir, suboxone and telithromycin for two weeks prior to the baseline visit and during the study period.
10. Subjects who are unwilling to refrain from using a tanning bed for 2 weeks prior to baseline and during the study
11. Subjects who have received oral roflumilast (Daxas®, Daliresp®) within the past 4 weeks
12. Subjects who cannot discontinue systemic therapies and/or topical therapies for the treatment of psoriasis prior to the baseline visits and during the study period according to the table below:

Excluded Medications and treatments	Wash out period prior to Day 1
Topical psoriasis medications (corticosteroids, calcipotriene, topical vitamin D derivatives, retinoids, anthralin, coal tar)	Cohort 1: 48 hours Cohort 2: 14 days
Systemic non-biologic treatments for psoriasis (apremilast, methotrexate, cyclosporine, azathioprine, corticosteroids)	Cohort 1: 48 hours Cohort 2: 28 days

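### Contraception is required only while the trial lasts, about 7 days past the last dose on the natural reading, while the protocol's own 28-day post-dose period covers only pregnancy plans at entry

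*Protocol*

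**What the plan says.** Inclusion criterion 6 (Protocol Section 8.9.1) states that "sexually active WOCBP must agree to use at least one form of highly effective contraception throughout the trial". It gives no period after the last dose.

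Exclusion criterion 6 (Section 8.9.2) bars pregnant and lactating women, and also "women planning to become pregnant during the study and / or within 28 days following the last dose of study medication". It therefore treats the study and the 28 days after dosing as two separate periods. Eligibility is checked only at Screening and Baseline (Cohort 1: Screening and Day 1) in the Section 6 flow charts, so this criterion acts on intentions at entry.

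Section 8.5 fixes how long a subject takes part:

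- Cohort 2: "the anticipated maximum duration of subject participation in Cohort 2 is 77 days", ending with a telephone call at Week 5 (Day 35 in the flow chart).
- Cohort 1: "the anticipated maximum duration of subject participation in Cohort 1 is 22 days", ending with "one follow up telephone call 7 days after the follow up visit". The flow chart puts this call on Day 8.

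The Synopsis adds that "Cohort 1 subjects will then be enrolled, if they meet entry criteria, into Cohort 2 of the study".

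The last scheduled pregnancy test in Cohort 2 is at Week 4. Section 8.16.1.3 allows follow-up for up to one month after treatment, but only for adverse events and clinically significant abnormal laboratory values. No visible section of the protocol or SAP sets a contraception period after the final call.

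**The concern.** The protocol recognises a 28-day period after the last dose in which pregnancy is to be avoided, yet the only rule attached to it is a question about plans at entry. That question does not reach an unplanned pregnancy or a later change of mind. Contraception does, and its visible requirement appears to stop first.

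A site that followed the text exactly could let a woman with no pregnancy plan at entry stop contraception about three weeks before the end of a period the protocol itself names. Section 8.1.2 describes this as the first study of the cream in humans, which is a reason to settle the point in the criteria rather than leave it to interpretation.

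**Working it through.** This is calendar arithmetic; no sample-size or error-rate calculation is involved.

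**Inputs**

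- Cohort 2: screening up to 6 weeks (42 days), daily dosing for 28 days, final call on Day 35 (Sections 6 and 8.5).
- Cohort 1: screening up to 14 days, one dose on Day 1, final call on Day 8 (Section 6) or 7 days after the Day 2 visit (Section 8.5).
- Window for Cohort 2 follow-up contacts: ±1 day (Section 6, footnote k).
- Post-dose period in exclusion 6: 28 days.

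**Assumptions.** The trial ends for a subject at her final call. The last dose is at the Day 28 visit in Cohort 2, or on Day 1 in Cohort 1 without rollover.

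**Check against the stated durations**

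- Cohort 2: 42 + 35 = 77 days, as stated.
- Cohort 1: 14 + 8 = 22 days, as stated. A Day 9 call (2 + 7) would give 14 + 9 = 23 days, which does not match, so Day 8 is the main case.

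Both stated durations therefore end at the final call, which supports the first assumption.

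**Days covered and not covered**

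Days covered = day of final call − day of last dose. Days not covered = 28 − days covered.

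| Case | Days covered | Days not covered |
|---|---|---|
| Cohort 2, as scheduled | 35 − 28 = 7 | 28 − 7 = 21 |
| Cohort 2, late last visit and early call | 34 − 29 = 5 | 28 − 5 = 23 |
| Cohort 2, early last visit and late call | 36 − 27 = 9 | 28 − 9 = 19 |
| Cohort 1 without rollover, flow chart | 8 − 1 = 7 | 28 − 7 = 21 |
| Cohort 1 without rollover, Section 8.5 wording | 9 − 1 = 8 | 28 − 8 = 20 |

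For a Cohort 1 subject who rolls over, the last dose and final call are those of Cohort 2, so the Cohort 2 rows apply.

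**How many subjects the Cohort 1 rows concern.** The Synopsis gives "Total subjects in both cohorts = 84-92", with 84 in Cohort 2. Subjects who do not roll over therefore number 84 − 84 = 0 to 92 − 84 = 8, men and women together.

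**Where a full 28 days would end.** Day 28 + 28 = Day 56 in Cohort 2 and Day 1 + 28 = Day 29 in Cohort 1, each 21 days after the scheduled final call.

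**The other reading of the term.** If the trial means the whole study, a woman whose final call falls 21 days or more before the study ends has no gap, and the last to finish keep the full 21 days. Her obligation would then depend on when she enrolled.

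**The case against.** The case for leaving the text alone has several parts.

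- **The two criteria serve different purposes.** Screening out declared intent with a wide margin, while requiring contraception during participation, is coherent. The 28 days is not presented as a contraception or washout standard, so 21 days is a shortfall only if the two periods ought to match. This is fair, and there is no contradiction. But the protocol gives no other reason for avoiding pregnancy in those 28 days, and contraception is what serves that aim for a woman who was not planning one.
- **The relevant text may be out of sight.** The consent form is not available, much of the nonclinical section is blacked out, and so are parts of the dose-selection and risk sections. A longer period, or the reason for a short one, may stand there. This stands as a limit. It does not change inclusion 6, which is legible and is the rule a site applies.
- **The end of the trial is inferred.** This is correct, and every figure above depends on it. A definition alone would remove the ambiguity, but defining it as the final call would leave the gap in place.
- **The remaining risk is small.** Pregnancy tests at Screening, Baseline and Weeks 1 to 4 control exposure during treatment. What is left is a woman with no plan at entry who stops a method within about three weeks of her final call. One with an intrauterine device or implant, or whose partner has had a vasectomy, would in practice stay covered. The Cohort 1 cases had one dose on 25 cm², and SAP Section 9.4 is worded as though that cohort had already finished. All of this stands and limits the weight of the point.
- **An amendment has a cost.** It does, and the cost is set out under the fix.

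**Conclusion.** The concern holds as a modest, inexpensive improvement to subject protection. On the reading that the trial ends at the final call, 7 of the 28 post-dose days carry a contraception requirement in Cohort 2 and 21 do not (19 to 23 with the windows). For the 0 to 8 Cohort 1 subjects who do not roll over, the gap is 21 days, or 20 on the Section 8.5 wording. A subject who withdraws early could have fewer covered days, since no visible text carries the obligation past withdrawal.

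These are calendar days without a visible requirement, not an estimate of pregnancy risk. The documents do not give the number of women of childbearing potential, so the affected group cannot be sized. They also do not show that 7 days is pharmacologically too short, after either 28 days of treatment on up to 5% of body surface or a single small application, and that is not claimed here. Confidence is medium, mainly because the consent form may already state a longer period.

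**What to change.** Extend inclusion criterion 6 so that contraception continues through the trial and for at least 28 days after the last dose, in line with exclusion criterion 6. If the sponsor's clinical team prefers another period, use that one period in both criteria. Confirm that the consent form agrees. Remind subjects at the existing final call, or at withdrawal for those who leave early. The same edit can correct the slip in the barrier-method sentence of inclusion 6, where conception is printed for contraception.

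The cost is one line of protocol text, a consent-form check and a reminder at a contact that already exists, with no added visit, test or analysis. Under Section 9.5.1 the amendment needs ethics approval for 8 sites in two countries ("7 sites in Canada; 1 site in the United States"), and it can be bundled with another amendment. If the consent form gives no period or a different one, it needs updating, and enrolled subjects may have to sign again. Affected women would use contraception for about three more weeks, including those on vehicle, because Cohort 2 is double blind.
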